### **7.2 Safety Analysis Set**

The safety analysis set will include all subjects who received at least 1 dose of talimogene laherparepvec.

**7.7 Subgroup Analyses**

See Section [4.2](#).

## **8. Interim Analysis and Early Stopping Guidelines**

No formal interim efficacy analysis is planned for this study. Interim safety analyses will be performed to support the evaluation of safety by the DLRT (see protocol section 10.3.2).

### **8.1 Primary Analysis**

**The primary analysis will occur 35 days after the last subject has enrolled and received at least 1 dose of talimogene laherparepvec.**

### **8.2 Final Analysis**

[figure not shown]
**The final analysis will occur when all the subjects have discontinued the study treatment and have had the opportunity to complete the long-term follow-up visit.**

## **9. Data Screening and Acceptance**

### **9.1 General Principles**

The objective of the data screening is to assess the quantity, quality, and statistical characteristics of the data relative to the requirements of the planned analyses.

### **9.2 Data Handling and Electronic Transfer of Data**

### **9.3 Handling of Missing and Incomplete Data**

Every effort will be made to obtain complete data in the clinical study. Partial or missing dates of adverse events and concomitant medications and incomplete death dates will be imputed. Details of the imputation algorithm are provided in [Appendix A](#), section 13. Adverse events with missing IP relatedness, seriousness, or CTCAE severity grades will be included in all analyses of TEAEs as long as the events qualify for the reporting period. Events with missing relatedness, seriousness, and severity grades will be excluded from corresponding analyses of TEAEs that are treatment-related, serious, and had a specific CTCAE grade.

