9.2.2 Adverse Events

9.2.2.1 Reporting Procedures for Adverse Events That Do Not Meet Serious Criteria

The investigator is responsible for ensuring that all adverse events observed by the investigator or reported by the subject that occur after first dose of talimogene laherparepvec through the safety follow-up visit (ie, 30 [+ 7] days after the last dose of talimogene laherparepvec) are reported using the Event CRF. Additionally, talimogene laherparepvec related adverse events that occur after the safety follow-up visit through the end of the long-term follow-up will be reported.

The investigator must assign the following adverse event attributes:

- Adverse event diagnosis or syndrome(s), if known (if not known, signs or symptoms),
- Dates of onset and resolution (if resolved),
- Severity (and/or toxicity per protocol),
- Assessment of relatedness to talimogene laherparepvec and,
- Action taken.

The adverse event grading scale used will be the CTCAE version 4.0. The grading scale used in this study is described in [Appendix A](#).

The investigator must assess whether the adverse event is possibly related to the talimogene laherparepvec. This relationship is indicated by a “yes” or “no” response to the question: Is there a reasonable possibility that the event may have been caused by the investigational product(s)?

The investigator is responsible for reviewing laboratory test results and determining whether an abnormal value in an individual study subject represents a clinically significant change from the subject’s baseline values. In general, abnormal laboratory findings without clinical significance (based on the investigator’s judgment) are not to be recorded as adverse events. However, laboratory value changes that require treatment or adjustment in current therapy are considered adverse events. Where applicable, clinical sequelae (not the laboratory abnormality) are to be recorded as the adverse event.

The investigator is expected to follow reported adverse events until stabilization or reversibility.

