9.2.2.2 Reporting Procedures for Serious Adverse Events

The investigator is responsible for ensuring that all serious adverse events observed by the investigator or reported by the subject that occur after signing of the informed consent/assent through 30 (+7) days after the last dose of talimogene laherparepvec are recorded in the subject's medical record and are submitted to Amgen. All serious adverse events must be submitted to Amgen within 24 hours following the investigator's knowledge of the event via the Event CRF. Additionally, talimogene laherparepvec related serious adverse events that occur after the safety follow-up visit through the end of the long-term follow-up will be reported.

If the electronic data capture (EDC) system is unavailable to the site staff to report the serious adverse event, the information is to be reported to Amgen via an electronic Serious Adverse Event Contingency Report Form within 24 hours of the investigator's knowledge of the event. See [Appendix B](#) for a sample of the Serious Adverse Event Worksheet /electronic Serious Adverse Event Contingency Report Form. For EDC studies where the first notification of a Serious Adverse Event is reported to Amgen via the eSerious Adverse Event Contingency Report Form, the data must be entered into the EDC system when the system is again available.

The investigator must assess whether the serious adverse event is possibly related to any study mandated activity or procedure. This relationship is indicated by a "yes" or "no" response to the question: "Is there a reasonable possibility that the event may have been caused by a study activity/procedure"?

The investigator is expected to follow reported serious adverse events until stabilization or reversibility.

New information relating to a previously reported serious adverse event must be submitted to Amgen. All new information for serious adverse events must be sent to Amgen within 24 hours following knowledge of the new information. The investigator may be asked to provide additional follow up information, which may include a discharge summary or extracts from the medical record. Information provided about the serious adverse event must be consistent with that recorded on the Event CRF.

If a subject is permanently withdrawn from protocol required therapies because of a serious adverse event, this information must be submitted to Amgen.

Approved

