10.5 Handling of Missing and Incomplete Data

Partial or missing dates of adverse events and concomitant medications will be imputed. Adverse events with missing severity and/or possible relationship to talimogene laherparepvec will be included in the all adverse events analyses, except by severity grade and treatment-related. Every effort will be made to obtain complete dates for deaths. Details of the imputation algorithms will be specified in the study-specific statistical analysis plan.

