### **10.6.2 Adverse Events**

The Medical Dictionary for Regulatory Activities (MedDRA) version **23.0** or later will be used to code all adverse events (AE) to a system organ class and a preferred term. The CTCAE version 4.0 will be used to grade severity of adverse events. In general, events with missing IP relatedness, seriousness, or CTCAE severity grades are included in the analysis of treatment emergent AE as long as the event meets the criteria for a TEAE. However, analyses of treatment-related, SAE, or grade 3 or higher, or combination thereof will exclude events with missing relatedness, seriousness, and severity grades, respectively.

The analyses for AEs will include TEAEs (ie, occurring in the treatment period) unless otherwise specified. The subject incidence of TEAEs will be summarized for all AEs, serious AEs, AEs leading to withdrawal of investigational product, grade 3 or 4 AEs, and fatal AEs. The subject incidence of all treatment-related AEs, serious AEs, AEs leading to withdrawal of investigational product, grade 3 or 4 AEs, and fatal AEs will be tabulated by system organ class (SOC) and preferred term in descending order of frequency. A listing of fatal AEs will be provided. A listing of all SAEs reported in the clinical database with an event onset from consent will be provided with onset reported relative to the first and most recent dose of study therapy and identification as a TEAE.

Subject incidence of DREs (disease-related events), fatal disease related events, serious disease-related events, and disease-related events leading to withdrawal from study will be tabulated by system organ class and preferred term.

Treatment-related AEs reported in long term follow-up will be summarized in this study and analyzed at a program-level.

Potential or known unintended exposure to talimogene laherparepvec, related suspected signs or symptoms, and detection of exposure to talimogene laherparepvec in a subject's household member, caregiver, or healthcare provider will be reported to Amgen. Exposures, signs or symptoms will be summarized in this study and analyzed at a program-level.

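### Leaving events with missing relatedness, seriousness or grade out of the corresponding TEAE tables can only understate those incidences

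*SAP*

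**What the plan says.** The rule has two halves. SAP 9.3 first retains the events: "Adverse events with missing IP relatedness, seriousness, or CTCAE severity grades will be included in all analyses of TEAEs", provided that they fall in the reporting period. It then removes them from the tables that need the missing attribute: "Events with missing relatedness, seriousness, and severity grades will be excluded from corresponding analyses of TEAEs that are treatment-related, serious". The sentence goes on to cover tables by CTCAE grade. SAP 10.6.2 says the same of the adverse event tables: "analyses of treatment-related, SAE, or grade 3 or higher, or combination thereof will exclude events with missing relatedness, seriousness, and severity grades, respectively".

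Protocol 10.5 has a narrower rule: "Adverse events with missing severity and/or possible relationship to talimogene laherparepvec will be included in the all adverse events analyses, except by severity grade", and likewise for the treatment-related analyses. It does not mention missing seriousness. SAP Section 11, which lists departures from the protocol's analyses, records only the change to the DLT analysis set.

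The tables concerned are subject incidences. SAP 10.1 puts all safety analyses other than DLT on the Safety Analysis Set, which SAP 7.2 defines as everyone who received at least one dose. SAP 3.2 plans 18 to 24 such subjects. Neither document plans to report how many events have a missing attribute, or to show a worst-case version of any table.

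**The concern.** Adverse event incidence is the named safety endpoint (protocol 10.1.1.3, SAP 4.1.3). The hypothesis in SAP Section 5 rests on the safety profile as well as on DLTs. In a small single-arm pediatric study, readers will look first at the treatment-related, serious and high-grade tables.

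For a subject incidence with a fixed denominator, omitting an event from the numerator has the same arithmetic effect in that table as deciding that the event does not qualify. The possible error therefore runs in one direction, the favourable one. Without a count of affected events, a reader could not tell whether the rule had changed a table. At this sample size, a single subject separates a report of no events from a report of one.

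**Working it through.** **Inputs**
- Denominator: Safety Analysis Set, 18 to 24 dosed subjects (SAP 7.2, 10.1, 3.2).
- Interval: exact Clopper-Pearson 95% (SAP 10.1).
- Frequency of missing attributes: not given in either document.

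**1. The plan's own figures.** The plan gives no figure for this rule. The nearest safety calculation is the probability of declaring a cohort safe with 6 DLT-evaluable subjects (protocol Table 5, SAP Table 2). Because 2/6 = 33.3% is not below 33%, safe means 0 or 1 DLT:

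P(safe) = (1 − p)^6 + 6p(1 − p)^5

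At p = 0.30 this is 0.1176 + 0.3025 = 0.420. For p = 10%, 20%, 30%, 40% and 50% it gives 88.6%, 65.5%, 42.0%, 23.3% and 10.9%. The plan states 89%, 66%, 42%, 23% and 11%, so the table reproduces to within a percentage point. It concerns DLTs and does not change under the present point.

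**2. Direction.** Let x be the number of subjects with a qualifying event, m the number whose only qualifying event has the missing attribute, and n the size of the Safety Analysis Set. The table reports (x − m)/n in place of x/n. Since m ≥ 0 and n is fixed, the reported value is never higher than x/n. The all-TEAE incidence does not depend on the attribute and is unchanged.

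**3. Size for one affected subject (m = 1, x = 1).** The shift is 100/n percentage points.

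| n | Reported under the rule | If the event is counted | Shift |
|---|---|---|---|
| 18 | 0/18 = 0% (0 to 18.5%) | 1/18 = 5.6% (0.1 to 27.3%) | 5.6 points |
| 24 | 0/24 = 0% (0 to 14.2%) | 1/24 = 4.2% (0.1 to 21.1%) | 4.2 points |

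The zero-event upper limits follow from 1 − 0.025^(1/n): 18.5% at n = 18 and 14.2% at n = 24. SAP 10.1 also asks for summaries by cohort, where n is smaller and the shift of 100/n is larger. The plan fixes no dosed number per cohort, so no single cohort figure is given here.

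**4. Average effect under assumed frequencies.** Suppose that a share s of qualifying subjects is lost through a missing attribute. This share is an assumption, and 2%, 5% and 10% are shown as a range. The reported incidence is the true incidence × (1 − s).
- True 30%: 29.4%, 28.5%, 27.0%.
- True 50%: 49.0%, 47.5%, 45.0%.

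Even at 10%, the average loss is 3 to 5 points. The practical risk is in sparse tables, where one subject decides between none and some.

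**The case against.** The strongest reply is that a residual blank should be rare and traceable.
- Protocol 9.2.2.1 makes severity and a yes/no relatedness judgement compulsory: "The investigator must assign the following adverse event attributes".
- Serious events have expedited reporting: "All serious adverse events must be submitted to Amgen within 24 hours".
- Data management checks for omissions and raises queries, and the investigator verifies the CRF (protocol 12.3).
- SAP 10.6.2 adds a safety net: "A listing of all SAEs reported in the clinical database with an event onset from consent will be provided". It also plans a listing of fatal events.
- The rule is prespecified and agrees with the protocol on severity and relatedness.

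Most of this stands, and it keeps the point small. It does not remove it. The SAP writes a rule for missing attributes, so it allows that some may remain. The all-TEAE tables keep these events but do not show the attribute at issue. The SAE listing will show a serious event with relatedness missing. An event whose seriousness is blank is not identified as an SAE, so the listing would not clearly include it.

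The objection also limits the remedy. Counting blank seriousness as serious in the main table would show SAEs that no investigator had reported as such, and the table could then disagree with the listing. Missing seriousness therefore belongs in a separate row.

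A reader might infer that the SAP recodes these events as unrelated or non-serious and so biases the safety tables as a whole. The text does not support that: it recodes nothing, and the all-TEAE tables are complete.

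**Conclusion.** The point holds for the treatment-related, serious and grade-specific TEAE tables only. The stated rule can understate those incidences and cannot overstate them, and no planned output would show that it had done so. The size is 5.6 points per affected subject at n = 18 and 4.2 at n = 24. This assumes that the missing field belongs to the subject's only qualifying event and stays missing after queries. How often that happens is unknown and probably low.

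Two further inferences are tempting and should not be drawn. The first is that the trial's primary conclusion is biased toward safe. DLT incidence is taken from the CRF in the DLT Analysis Set (SAP 10.6.1), and a dose is declared safe on the DLT rate. The missing-attribute rule for TEAE tables does not govern either. The second is that one subject is worth 11.1 points, from 1/9. Nine is the minimum number of DLT-evaluable subjects in cohort A1, not the denominator of an adverse event table.

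This is a minor weakness, but in a named safety endpoint of a small trial, and cheap to correct.

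**What to change.** In SAP 9.3 and 10.6.2:
- Count a TEAE whose relatedness is still missing after queries as treatment-related. Apply this also in the combined tables, such as treatment-related serious events.
- For missing seriousness or CTCAE grade, leave the main table as planned. Add a worst-case row that counts these events as serious, or as grade 3 or higher.
- Footnote each affected table with the number of events handled in this way, including when it is zero.

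In SAP Section 11, record the departure from protocol 10.5 on relatedness, and note that the SAP also covers missing seriousness, on which protocol 10.5 is silent. Recording it there keeps the change within the SAP.

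The cost is SAP wording, one extra row in the tables concerned and a footnote. The downside is a possible slight overcount of treatment-related events, which the footnote would make visible. The DLT analysis and the all-TEAE tables do not change.

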### **9.4 Detection of Bias**

Lack of protocol compliance may introduce potential bias in the estimation of protocol endpoints. All important protocol deviations (IPDs) will be reported, documented and stored in eClinical (a clinical trial management system). IPDs will be regularly reviewed in the study team's IPD review meetings as well as before analysis.

Protocol compliance will be examined by tabulating subjects with IPDs.

## 9.5 Outliers

Descriptive statistics will be used to identify outliers in any key variables. Suspected outliers will be included in all analyses unless there is sufficient scientific justification to exclude them.

## 9.6 Distributional Characteristics

All binary endpoints will be assumed to follow a binomial distribution. The Kaplan-Meier estimates for the probability of time-to-event endpoints are non-parametric.

## 9.7 Validation of Statistical Analyses

Programs will be developed and maintained, and output will be verified in accordance with current risk-based quality control procedures.

Tables, figures, and listings will be produced with validated standard macro programs where standard macros can produce the specified outputs.

The production environment for statistical analyses consists of Amgen-supported versions of statistical analysis software; for example, the SAS System version 9.2 or later.

## 10. Statistical Methods of Analysis

### 10.1 General Principles

The DLT Analysis Set will be used to summarize the subject incidence of DLT and the Safety Analysis Set will be used for all other analyses of safety and efficacy endpoints.

Descriptive statistics will be provided for efficacy, safety, talimogene laherparepvec DNA, and other exploratory endpoints for all subjects and by cohort. Summary statistics including mean, standard deviation, median, first and third quartiles, minimum and maximum will be provided for continuous variables. Frequency and percentage will be summarized for binary and categorical variables. Proportions and the corresponding exact 95% confidence intervals using F distributions will be calculated (Clopper & Pearson 1934). Exact tests will be considered for subgroup analyses. Time to-event endpoints will be estimated using the K-M method.

Separate reporting at a program-level may occur of close contact and HCP events with or without a known unintended exposure.

### 10.2 Subject Accountability

The number of subjects enrolled will be tabulated by countries and investigator sites overall and by cohort (based on age). Subject disposition (including the number

screened, enrolled, treated, ended treatment, that completed the safety follow-up visit, and that completed the study) will be summarized separately for all enrolled subjects. Reasons for not receiving treatment, for ending treatment, not completing the 30-day safety follow-up visit, and ending the study will be provided.

### 10.3 Important Protocol Deviations

Important Protocol Deviations (IPDs) categories are defined by the study team before the first subject's visit and updated during the IPD reviews throughout the study prior to database lock. These definitions of IPD categories, sub-category codes, and descriptions will be used during the course of the study.

Eligibility deviations are defined in the protocol. Eligibility deviations that are defined as IPDs will be summarized in both the IPD and Eligibility Deviation table and IPD and Eligibility Deviation listings.

### 10.4 Demographic and Baseline Characteristics

Summary statistics of the following demographic and baseline characteristics will be tabulated using the Safety Analysis Set.

- Age at baseline: (2 to < 12 years, 12 to ≤ 21 years)
- Sex (female versus male)
- HSV-1 baseline serostatus (positive versus negative)
- Baseline sum of largest diameter of target lesions
- Extent of disease (localized versus metastatic)
- Performance status (Karnofsky/Lansky play scale (70% versus > 70%))
- Prior lines of therapy in the recurrent/metastatic setting (0,1, 2, > 2)
- Prior surgery for current malignancy (yes versus no)
- Prior radiotherapy for current malignancy (yes versus no)
- Complete surgical resection of all gross diseases (yes versus no)
- Other covariates reported in the literature or from other Amgen studies maybe considered in the analysis as appropriate and if feasible at the time of analysis.

### 10.5 Efficacy Analyses

[figure not shown]
#### 10.5.1 Analyses of Secondary Endpoints - ORR, DOR, TTR, TTP, PFS, OS

[figure not shown]
Analysis of secondary endpoints such as ORR, DOR, TTR, TTP, PFS, OS will be based on Safety Analysis Set and excluding subjects without baseline measurable disease, if applicable.

- ORR (CR+PR) will be summarized with associated exact 95% CIs for binomial proportions (Clopper & Pearson 1934).

- DOR among responders, TTP, PFS and OS will be estimated using the Kaplan-Meier method and estimates of event time quartiles, event-free rates at selected times and the corresponding 95% CIs will be provided.
- Summary statistics will be estimated for TTR among responders.

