3.1.1.2 Long-term Follow-up

After the safety follow-up visit, all subjects will enter the long-term follow-up. Subjects will be followed for survival and use of subsequent anticancer therapies every 12 weeks (\pm 28 days) from the safety follow-up until death, subject or legally acceptable representative withdraws full consent/assent, or up to approximately 24 months after the last subject is enrolled in the study. In addition, talimogene laherparepvec-related adverse events that occur through the end of the long term follow-up will be reported.

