10.4.1 Primary Endpoint

The DLT analysis set will be used to summarize the subject incidence of DLTs for the study and the safety analysis set will be used for all other analyses of safety endpoints. The efficacy analysis will be conducted using the safety analysis set unless otherwise specified.

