10.4.2 Secondary Endpoints

Efficacy Endpoints:

ORR, DOR, TTR, TTP, PFS, and OS will be summarized in the overall population. ORR will be summarized with an associated exact 95% CI using the safety analysis set and excluding subjects without baseline measurable disease, if applicable. DOR among responders, TTR, TTP, PFS and OS will be estimated using the Kaplan-Meier method.

Safety Endpoints

Subject incidence of treatment-emergent and treatment-related adverse events will be summarized. **Treatment-emergent adverse events are defined as any adverse event occurring after first dose through 30 days after last dose of talimogene**

laherparepvec. Treatment-related adverse events are defined as treatment-emergent adverse events which are considered to be related to the treatment of talimogene laherparepvec, as determined by the investigator. Medical Dictionary for Regulatory Activities (MedDRA) will be used to code adverse events to a system organ class (SOC) and a preferred term within the SOC. The CTCAE version 4.0 will be used to grade severity of adverse events. In addition, clinically significant laboratory changes and clinically significant changes in vital signs will be summarized with descriptive statistics.

Subject incidence of all disease-related events, fatal disease-related events, serious disease-related events, and disease-related events leading to withdrawal from study drug will be provided.

[figure not shown]
A summary of deaths after initiation of the study through 30 days since the last dose of talimogene laherparepvec will be provided.

Summary statistics will also be provided for concomitant medications, dose delay, study drug discontinuation, overall exposure, and Karnofsky performance status and Lansky play scale.

[figure not shown]
Potential or known unintended exposure to talimogene laherparepvec, related suspected signs or symptoms, and detection of exposure to talimogene laherparepvec in a subject's household member, caregiver, or healthcare provider will be reported.

Summary statistics will be provided for vital signs, physical measurements and laboratory data. Details of the analysis will be provided in statistical analysis plan.

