## 6. Definitions

### 1-year, 2-year survival

The Kaplan-Meier (K-M) estimate of the proportion of subjects alive at 1 year and 2 years, respectively.

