**Overall Survival (OS)**

OS is defined as the interval from first dose to the event of death from any cause; otherwise, OS is censored at the date the subject was last known to be alive.

[figure not shown]

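### SAP 10.5.1 extends the measurable-disease exclusion to a list that names OS, while the protocol attaches it to ORR only and OS does not depend on measurability

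*SAP*

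**What the plan says.** **SAP 10.5.1** sets one population for all six secondary endpoints: "ORR, DOR, TTR, TTP, PFS, OS will be based on Safety Analysis Set and excluding subjects without baseline measurable disease, if applicable".

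**Protocol 10.4.2** places the exclusion in a sentence about ORR alone: "ORR will be summarized with an associated exact 95% CI using the safety analysis set and excluding subjects without baseline measurable disease, if applicable". The sentence after it gives the Kaplan-Meier method for DOR, TTR, TTP, PFS and OS and contains no exclusion.

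**Default population.** Protocol 10.4.1 says "The efficacy analysis will be conducted using the safety analysis set unless otherwise specified". SAP 10.1 agrees: "the Safety Analysis Set will be used for all other analyses of safety and efficacy endpoints". In both documents that set is every subject with at least one dose, with no condition on lesion size.

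**OS.** SAP Section 6 says "OS is defined as the interval from first dose to the event of death from any cause". The same section defines 1- and 2-year survival as the Kaplan-Meier "estimate of the proportion of subjects alive at 1 year and 2 years, respectively". Protocol 3.1.1.2 says that, after the safety visit, "all subjects will enter the long-term follow-up".

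**Declared changes.** SAP Section 11 lists one departure from the protocol, the definition of the DLT analysis set.

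**The concern.** Excluding subjects who have no measurable lesion at baseline makes sense for ORR. Under protocol Appendix D, Table 7, footnote f, such a subject is always unevaluable and so cannot be a responder. That reason does not carry over to OS, where vital status is known whether or not a lesion could be measured.

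Taken at its word, the SAP sentence would remove eligible, dosed subjects, with their follow-up time and any deaths, from the OS curve and from the 1- and 2-year estimates. The protocol does not ask for this, and the SAP does not declare it as a change. The choice of OS denominator would then rest on how a programmer understands *if applicable*.

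**Working it through.** The plan gives no figure on this point to reproduce. The check compares the texts and then illustrates the possible size.

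**1. Which endpoints carry the exclusion?**

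| Endpoint | Protocol 10.4.2 | SAP 10.5.1, literal | Does measurability matter? |
|---|---|---|---|
| ORR | excluded | excluded | Yes: always unevaluable |
| DOR, TTR | none stated | excluded | No practical difference: responders only, and these subjects cannot respond |
| TTP | none stated | excluded | Essentially none: no progression event is possible |
| PFS | none stated | excluded | Arguable either way |
| OS | none stated | excluded | No: the event is death |

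On PFS, excluding these subjects loses their deaths. Keeping them means that they contribute only deaths, because SAP Section 6 censors at the last evaluable assessment, an evaluable assessment is one not rated UE, and these subjects have none. Either population is defensible. OS is the only endpoint where the exclusion has no rationale.

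**2. Can the excluded group exist?** Yes. Inclusion criterion 113 accepts measurable or non-measurable lesions. Criterion 106 can be met by several injectable lesions that reach 10 mm only in aggregate, by a node with a short axis under 15 mm, or by a lesion in an irradiated area without demonstrated progression. Under Appendix D none of these counts as measurable. A subject who enters by such a route may still have a measurable lesion elsewhere, so this shows possibility, not frequency.

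**3. How large could the effect be?** Inputs:
- N = 18 or 24 dosed subjects (protocol 10.2, SAP 3.2).
- Survival at the time point in the full set: 50%, so s = 9 or 12 alive (assumption).
- No censoring before the time point (assumption).
- m excluded subjects: not given in the documents; 0 to 3 shown (assumption).

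Formulas: the estimate becomes s/(N − m) if all excluded subjects had died, and (s − m)/(N − m) if all were alive.

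| N | m | Excluded all died | Excluded all alive |
|---|---|---|---|
| 18 | 0 | 9/18 = 50.0% | 9/18 = 50.0% |
| 18 | 1 | 9/17 = 52.9% | 8/17 = 47.1% |
| 18 | 2 | 9/16 = 56.3% | 7/16 = 43.8% |
| 18 | 3 | 9/15 = 60.0% | 6/15 = 40.0% |
| 24 | 0 | 12/24 = 50.0% | 12/24 = 50.0% |
| 24 | 1 | 12/23 = 52.2% | 11/23 = 47.8% |
| 24 | 2 | 12/22 = 54.5% | 10/22 = 45.5% |
| 24 | 3 | 12/21 = 57.1% | 9/21 = 42.9% |

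For comparison, the Clopper-Pearson 95% CI is 26.0% to 74.0% for 9/18 and 29.1% to 70.9% for 12/24. One excluded subject shifts the estimate by 2.9 points at N = 18 and 2.2 points at N = 24, in either direction. Both are small against the sampling uncertainty.

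**The case against.** The strongest reply is that *if applicable* already settles the matter: the exclusion applies where measurability is relevant, and OS is therefore spared. SAP 10.1 supports this by assigning the full set to efficacy endpoints. So does SAP Section 1, which presents the plan as detailing the analyses in protocol amendment 3, and so does the absence of any OS entry in Section 11. Together these suggest that no change of OS population was intended.

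That reading is possible, but the text does not secure it. The same two words close the protocol's sentence on ORR alone, where they most naturally mean *if any such subjects exist*. Carried into a sentence naming six endpoints, that meaning takes the subjects out of OS. The SAP's specific sentence also sits against its own general rule, and nothing says which prevails for OS.

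The reply does stand on size: the count is unknown, the figures above follow from assumed counts, and no trial decision depends on OS.

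A reader might infer two stronger points, and the documents support neither:

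- **That the protocol expressly promises OS without the exclusion**, because it says "ORR, DOR, TTR, TTP, PFS, and OS will be summarized in the overall population". Protocol 10.4 uses the term for the pooled cohorts as opposed to each cohort separately. ORR is in the same list and still carries the exclusion in the next sentence, so the phrase does not define an analysis set.
- **That the SAP is also wrong for PFS and TTP.** The literal wording does go beyond the protocol there, but TTP is essentially unaffected and either PFS population can be defended.

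**Conclusion.** The point holds for OS, as a minor one. The SAP sentence, followed literally, gives OS a population that the protocol does not specify and that has no rationale for an all-cause death endpoint. It does not prove that OS will be analysed on the reduced set, because *if applicable* leaves room for the intended result.

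The effect is nil if every dosed subject has measurable disease. Otherwise, under the stated assumptions of 50% survival and no early censoring, it is about 3 points per excluded subject at N = 18, well inside the 26% to 74% interval. OS is descriptive here. The DLT analysis and the decisions on cohorts use the DLT-evaluable subjects and are untouched.

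**What to change.** In SAP 10.5.1, replace the single population sentence with one that separates the endpoints, for example: *The restriction to subjects with measurable disease at baseline applies to ORR; DOR and TTR are computed among responders and follow from it. OS, including the 1- and 2-year estimates, uses the full Safety Analysis Set.* This matches protocol 10.4.1 and 10.4.2 and SAP 10.1, so Section 11 needs no entry for OS.

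As an optional clarification, name the PFS and TTP population in the same place. If a restriction to measurable disease is intended there, list it in Section 11 as a departure from the protocol.

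The cost is one or two SAP sentences, with no new data and no protocol amendment.
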